Date: 09/19/2019

Title: Potato Research for Enhancing Metabolic Outcomes

ClinicalTrials.gov Identifier: NCT04203238

Meat and Potato Diet for Enhancing Cardiometabolic Health in Adults

PI Name: [name].

Co-Investigator: [name]., R.D.

Medical Investigator: [name].

Protocol Version Date: September 16, 2019

ABSTRACT

Background

The potato is a nutritious food that comprises approximately 30% of total vegetable intake in the United States (US). Consumption of pulses in the US is low but its contribution to health is frequently promoted. However, in the US diet, potatoes contribute as much dietary fiber, far more potassium, and a host of similar nutrients as pulses. When prepared to enhance its slowly digested starch content, potatoes produce a moderate glycemic response. In encouraging a shift towards plant-based foods and sustainable diets, the potato can partially replace meat in meat dishes to enhance the overall quality of the diet and reduce meat intake to recommended levels.

Design and Methods

Aim. The aim of the proposed trial is to compare the effect of healthy eating patterns containing potato and lean meat (PLM) in the ratio 40:60 + starchy staple (potato), and pulses and lean meat (LMP) in the ratio of 40:60 + starchy staple (bread, rice, pasta) for eight weeks on the glycemic response, lipid profile, and an inflammatory biomarker (high sensitivity C-reactive protein (hsCRP) in 36 overweight or obese, insulin resistant adults.

Hypothesis. We hypothesize that the PLM and LMP diets will improve blood glucose and lipid responses, and hsCRP compared to baseline, and will be non-inferior each other.

Study Design. We propose to conduct a randomized, controlled, parallel trial. Subjects who satisfy inclusion/exclusion criteria will report to the Pennington Biomedical Research Center (PBRC) in the morning after an overnight fast. Weight and vital signs will be measured and an intravenous catheter will be inserted in the arm to obtain baseline blood samples for measurement of glucose, insulin, lipids, LDL particle size, and high sensitivity C-reactive protein (hsCRP). Subjects will be randomly assigned to receive the PLM or LMP meals and complete a meal tolerance test (MTT) measuring glucose and insulin over three hours.

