- Measurement of height, metabolic weight, waist circumference, vital signs (blood pressure, pulse, and temperature).
- Recording of concomitant medication use.
- Urine specimen collection for urine human chorionic gonadotropin (HCG) (for pregnancy in women of child bearing potential).
- Blood collection for insulin, complete blood count (CBC), and Chemistry 15 panel.

Baseline (5 hours; fasting for at least 8 hours)

To start the study, eligible subjects will arrive at the clinic in the morning following an overnight fast (except for water) that began no later than 8 hours prior to the study appointment. The following procedures will be performed:

- Measurement of metabolic weight and vital signs (blood pressure, pulse, and temperature).
- Blood collection for measurement of lipids and hsCRP.
- Three-hour meal tolerance test (MTT) with glucose and insulin.
- Recording of adverse events.
- Recording of visual analog scale (VAS) ratings of satiety measures
- Nutrition counseling session with registered dietitian.
- Dispensation of foods for one week.

Visits 2 to 4 (1 hour to 1½ hours)

Subjects will report to the clinic and the following procedures will be performed.

- Measurement of weight
- Collection of all containers, and any uneaten food items and assessment of compliance.
- Nutrition counseling session with registered dietitian.
- Dispensation of foods for one week.
- Recording of adverse events.

Visit 5 (1 hour to 1½ hours; fasting for at least 8 hours)

Subjects will arrive at the clinic in the morning following an overnight fast (except for water) that began no later than 8 hours prior to the study appointment. The following procedures will be performed:

- Measurement of metabolic weight.
- Collection of all containers and any uneaten food items and assessment of compliance.
- Dispensation of foods for one week.
- Recording of adverse events.

Nutrition counseling session with registered dietitian will be via the telephone.

Visit 6 - 8 (1 hour to 1½ hours)

Subjects will report to the clinic and the following procedures will be performed.

- Measurement of weight
- Collection of all containers and any uneaten food items and assessment of compliance.
- Dispensation of foods for one week.
- Recording of adverse events.

Nutrition counseling session with registered dietitian will be via the telephone.

Visit 9 (4 hours; fasting for at least 8 hours)

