Nutrition Counseling. Subjects will be counseled on adhering to the diet plan by a PBRC dietitian. The PBRC dietitians specialized in counseling have extensive experience in advocating behavior change messages to subjects instructed to follow structured meal plans. The counseling sessions will be held once per week for 30-60 minutes as needed. For the first four weeks, the subjects will meet with the dietitian followed by four weekly sessions over the telephone. Counseling sessions will focus on identifying barriers to adhering to the diet plan, problem-solving, and how to be compliant on occasions when subjects may have to eat out.

Meal Tolerance Test (MTT). Following a fast which began no later than eight hours before the appointment, an intravenous line will be placed in the arm vein and blood will be drawn for baseline (time 0) glucose and insulin measurement, following standard procedures. Subjects will then receive the PLM or LMP meal according to the randomization assignment. Blood will be collected through the intravenous line at 30, 60, 90, 120, and 180 minutes following the meal for measurement of glucose and insulin.

Biochemical Assessments. Chemistry 15 panel, CBC, fasting insulin, lipid profile, and hsCRP measurements will be performed according to standard PBRC procedures for IV line/blood draws and the relevant measurement. The LDL particle size will be measured using nuclear magnetic resonance (NMR) spectroscopy at LabCorp (Morrisville, NC) in samples collected at and shipped from PBRC.

See Appendix 1 for a detailed listing of all blood draws and their required blood volumes.

Appetite Ratings. A questionnaire (VAS) will be administered at each of the time-points that blood is drawn during the meal tolerance test at baseline and at Visit 9. Subjects will be asked to rate their appetite by making a mark on the line at the point that best represents their feelings at the time that they complete the questionnaire (Appendix 2).

Adverse Events. An Adverse Event (AE) is defined as any untoward medical occurrence in a patient or clinical investigation subject, temporally associated with the subject's participation in research. We define AE as any unfavorable and unintended sign (including a clinically significant abnormal laboratory finding), symptom, or disease (new or exacerbated) temporally associated with the subject's participation in research.

DATA SAFETY MONITORING PLAN

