Power and Sample Size. Power for this study is based on a parallel arm design with the potato/lean meat diet (PLM) and pulses/lean meat diet (LMP) groups. Equivalence in blood glucose will be the primary outcome. A similar crossover study by Hatonen *et al.*,⁴³ using 11 subjects, showed that adding meat, fat, and vegetables to a potato meal reduces the incremental area under the curve for glucose (iAUC) in a MTT. The iAUC was lower after the mixed meal ($96 \pm 12.5 \text{ mmol} \times \text{min/L}$) than after potato alone ($197 \pm 28.2 \text{ mmol} \times \text{min/L}$). Long interventions using crossover designs with washout periods are associated with high dropout rates.⁵⁸ In our experience, recruitment rates are slow and drop-out rates are high, especially, when there is no symptomatic improvement that is obvious to subjects participating in the trial. Therefore, we will use an eight-week parallel arm design.

We assume the standard deviation estimates from the study by Hatonen *et al.* to be similar to this proposed study since the PLM and LMP daily diets will also reduce the meat content in an overall healthy eating pattern which has been shown to lower the glycemic or insulinemic responses.^{50,59,60} Further, our trial is a controlled feeding study in which all meals are provided and compliance is tightly monitored by registered dietitians. This study has 80% power to show equivalence between the two groups with at least 15 subjects per group given that the difference between the two groups is no larger than 40 mmol \times min/L. Allowing for approximately 20% loss to follow-up, or 3 subjects per group, this study will enroll a total of 36 subjects.

Statistical Analysis. The secondary outcomes are changes in insulin, lipid concentrations, LDL particle size, and hsCRP. Mixed effect linear models will all be used to estimate changes across the eight weeks for primary and secondary outcomes. Normality of model residuals will be checked and transformation will be applied where necessary. An unstructured covariance matrix will model the within-subject effects. Missing data is assessed using a sensitivity analyses which will use several different sets of models under different assumptions. Covariates, like age, race, and gender will be determined using Akaike information criterion (AIC) as the model fit criteria.

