LDL particle size		1.5	1.5
Glucose and Insulin (MTT)		15	12.5
Total	8	21	22

Notes: (1) Chemistry 15 includes fasting glucose and lipids (2) IV blood draw volumes include 0.5 ml returned during blood draw.

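### The plan does not specify adjusting the diet contrasts for each fasting secondary outcome's own pre-diet value; doing so would usually gain precision from data already collected

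*Combined protocol and SAP*

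**What the plan says.** Statistical Considerations, Statistical Analysis, defines the secondary endpoints as changes: "The secondary outcomes are changes in insulin, lipid concentrations, LDL particle size, and hsCRP". The model is given in two sentences: "Mixed effect linear models will all be used to estimate changes across the eight weeks for primary and secondary outcomes" and "An unstructured covariance matrix will model the within-subject effects". On covariates it says: "Covariates, like age, race, and gender will be determined using Akaike information criterion (AIC) as the model fit criteria". The fixed effects and the diet contrast are not written out. The outcome's own baseline value is neither named as a covariate nor excluded, and nothing is said about constraining baseline means to be equal between diets.

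The pre-diet fasting values are collected. Table 1 schedules lipids, LDL particle size and hsCRP at Baseline and Visit 9, and the Baseline visit list includes "Blood collection for measurement of lipids and hsCRP". In the meal tolerance test, "blood will be drawn for baseline (time 0) glucose and insulin measurement" before the assigned meal is served. Table 1 also schedules insulin and the Chemistry 15 panel at Screening, and the notes to Appendix 1 state: "Chemistry 15 includes fasting glucose and lipids". Insulin and lipids therefore have two pre-diet values. LDL particle size and hsCRP have one.

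**The concern.** A within-subject covariance needs at least two responses per subject. These outcomes are compared at Baseline and Visit 9, so the natural reading is that Baseline enters the model as a response. If each diet then has its own baseline mean, the diet-by-time term is the difference in raw change. The fasting Baseline values precede the first assigned meal, so their arm means differ only by chance, and a model that uses this fact is usually more precise.

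Leaving the matter to AIC does not settle it. AIC could keep the baseline value for one outcome and drop it for another, after the data are seen. What is at stake is the width of the intervals for the Aim 2 diet contrasts in a trial of 36 subjects. Aim 2 predicts no difference between diets on these outcomes, so avoidable imprecision makes the predicted result easier to obtain by default.

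**Working it through.** **Plan's own figure.** The documents give no power or precision figure for any secondary outcome. The stated 15 per group refers to glucose iAUC. It cannot be reproduced from the printed inputs, because neither alpha nor the SD used is stated. It enters here only as the number of completers.

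**Inputs.** Completers per arm n = 15, so N = 30; enrolled per arm 18 (both from the protocol). Correlation r between Baseline and Visit 9: not given, assumed 0.5 to 0.95. Equal variance s² at each visit: assumed.

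**Step 1: what the usual model estimates.** In one simulated pre/post data set (15 per arm, r = 0.6), a mixed model with free baseline means gave a diet-by-time estimate of -0.0138, identical to the raw difference in mean change. Constraining the baseline means gave -0.1192, close to the ANCOVA estimate of -0.1188, and the standard error fell from 0.403 to 0.338. That is one data set; the expected gain follows.

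**Step 2: expected precision, Baseline adjustment.**

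- Var(difference in change) = (2/n) · 2s²(1 - r)
- Var(adjusted difference) = (2/n) · s²(1 - r²) · [1 + 1/(N - 4)], where the bracket is the cost of estimating the slope: 1 + 1/26 = 1.038
- Variance ratio = [(1 + r)/2] · 1.038

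At r = 0.5: 0.75 × 1.038 = 0.779, and √0.779 = 0.88. Break-even is at (1 + r)/2 = 26/27, so r = 0.926.

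**Step 3: adding the Screening value (insulin, lipids).** Assume the same r between all three visits. The residual variance is s²(1 - r)(1 + 2r)/(1 + r). The small-sample factor for two covariates is 1 + 2/25 = 1.08. The variance ratio to the change score is [(1 + 2r)/(2(1 + r))] · 1.08. At r = 0.5: 0.667 × 1.08 = 0.72, and √0.72 = 0.85.

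| Assumed r | SE ratio, Baseline only | SE reduction | SE ratio, Baseline + Screening |
|---|---|---|---|
| 0.5 | 0.88 | 12% | 0.85 |
| 0.7 | 0.94 | 6% | 0.87 |
| 0.8 | 0.97 | 3% | 0.88 |
| 0.9 | 0.99 | 1% | 0.89 |
| 0.95 | 1.01 | none | 0.90 |

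Simulation with 15 per arm agrees. For Baseline only, 20,000 runs gave 0.876, 0.937, 0.990 and 1.006 at r = 0.5, 0.7, 0.9 and 0.95. With the Screening value added, simulated ratios lay between about 0.84 and 0.90.

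**Step 4: chance imbalance.** With 15 per arm the baseline difference has SD √(2/15) = 0.365 baseline SDs. Given an imbalance, the change contrast is shifted by -(1 - r) times it: for a one-SD imbalance, 0.18 SD at r = 0.5 and 0.07 SD at r = 0.8. The variance of this shift is (2/n)s²(1 - r)². Before the slope-estimation cost, that is exactly the gap between the two variances in Step 2: 2(1 - r) - (1 - r²) = (1 - r)². It is the same loss seen conditionally, not a second one.

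**The case against.** The strongest reply is that the plan is silent rather than wrong. The reduction to raw change rests on free baseline means, which the text never states. The covariate list is introduced by examples and excludes nothing. A common-baseline model is itself a mixed model with unstructured covariance that estimates change, so it fits the plan as written. All of this stands. A reader might infer that the plan rules out baseline adjustment or makes no use of the pre-diet values; the documents do not support that. Baseline values are used to form the changes, and screening glucose and insulin serve the eligibility rules. What is missing is a stated adjustment of the diet contrast.

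Three other stronger readings also fail.

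- That every fasting contrast loses precision. With Baseline adjustment alone, the gain disappears above r of about 0.93, and the documents give no r for any outcome.
- That the change score is biased. It is unbiased over randomisation; Step 4 describes only a shift conditional on the observed imbalance.
- That the gain equals 33%, 18% and 11% more subjects at r = 0.5, 0.7 and 0.8. Those figures follow from the large-sample ratio (1 + r)/2. At 15 per arm the factors are 1/0.779, 1/0.883 and 1/0.935, or about 28%, 13% and 7%.

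Two cautions on the remedy are also fair. Selection on HOMA-IR above 2 and fasting glucose below 126 mg/dL may restrict the range of Screening values and weaken them as covariates. And ANCOVA of Visit 9 alone does not directly give the within-group changes that Aim 2 also hypothesises.

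**Conclusion.** The point holds as a missing pre-specification with a better method available from data already collected. The plan does not fix how each fasting secondary's pre-diet value enters the diet contrast, and the usual reading of its model gives raw change. At 15 completers per arm, Baseline adjustment would reduce the standard error by about 12% at r = 0.5, falling to 1% at 0.9 and to nothing above about 0.93. For insulin and lipids, adding the Screening value would put the standard error about 10 to 16% below that of the change score, if correlations are equal among visits and selection does not weaken the Screening value. These sizes rest on assumed correlations and equal variances. The exact equality with raw change also requires complete pre/post data.

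The finding concerns secondary outcomes only. It does not extend to the primary glucose iAUC: the baseline meal test is done with the assigned meal, so its area is not a pre-treatment value.

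**What to change.** For fasting insulin (meal-test time 0), lipids, LDL particle size and hsCRP, state one of the following in advance and keep it outside AIC selection:

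- a mixed model with a common baseline mean for both diets and the diet difference estimated at Visit 9, which also provides the within-group changes that Aim 2 needs; or
- ANCOVA of Visit 9 on Baseline for the between-diet contrast, with the within-group changes reported separately.

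For insulin and Chemistry 15 lipids, add the Screening value as a second pre-diet covariate. Where an outcome is transformed, put its pre-diet values on the same scale. State that the common-baseline constraint does not apply to the meal-test glucose or insulin areas.

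The cost is a few sentences in the analysis plan and one or two degrees of freedom. No new data are needed. If r is very high, Baseline adjustment alone costs almost nothing: at r = 0.95 the standard error rises by about 0.6%.

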Following baseline testing, subjects will receive foods each week over eight weeks. All diets will be designed to maintain body weight. PLM and LMP diets will include wholegrains, fruits, vegetables, nuts, seeds, and five ounces of meat/day with the respective substitutions and starchy staples as the main entrées at lunch and dinner. Subjects will be required to eat only the study foods and will be counseled by a dietitian on adhering to the study protocol. Subjects will report to the PBRC weekly to collect the study foods and will receive nutrition counseling. Compliance will be evaluated by the dietitian through monitoring of all foods and containers that subjects will be required to return. Weight and vital signs will be measured weekly. At week nine, baseline testing will be repeated and compliance with the diet will be evaluated. Adverse events will be recorded during the study. It is our expectation that the approach used in this study will provide evidence that in the context of an overall healthy eating pattern, potatoes and pulses will reduce the glycemic and insulinemic responses, lipid profile, and hsCRP concentration but will be non-inferior to each other.

These results will be significant, in that they will potentially provide a cost-effective intervention that will substantially improve the health and quality of life for the growing number of overweight or obese individuals who have developed insulin resistance, and prevent or slow the progression to diabetes.

DESCRIPTION AND RATIONALE

Insulin Resistance

The impaired effect of insulin on regulation of blood glucose characterizes the condition known as insulin resistance.¹ Estimates from the Centers for Disease Control and Prevention suggest that more than one in three US adults (33.9%) have prediabetes,² an insulin resistant state that

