The objective of the present application is to develop a diet intervention to reverse insulin resistance in an overweight or obese population. For US adults, the white potato ranks among the top 15 foods providing key nutrients such as potassium and dietary fiber.²³ Pulses are a highly recommended food that contribute as much dietary fiber to the diet of US adults as potatoes.⁵³ Our central hypothesis is that in the context of an overall healthy eating pattern, potatoes and pulses will not differ in the glycemic and insulinemic responses, lipid profile, and hsCRP concentration they elicit. The rationale for the proposed study is that by developing a small changes sustainable approach to reducing meat intake and reducing the glycemic load of the diet, we can slow and ultimately prevent the progression to diabetes in individuals with untreated insulin resistance. We plan to test our hypothesis and accomplish the objective of this application by pursuing the following specific aims:

Aim 1. Compare the effect of diets containing white potato/lean meat (PLM) and pulses/lean meat (LMP) main entrées for eight weeks on the glycemic response in 36 overweight or obese, insulin resistant adults. This aim requires a randomized controlled feeding trial of potato and lean meat in the ratio 40:60 + starchy staple (potato), and pulses and lean meat (40:60) + starchy staple (bread, rice, pasta). The primary outcome is the glycemic response to the diets.

Hypothesis. The mean glycemic response will improve compared to baseline in the PLM and LMP groups but the two diets will be non-inferior to each other.

Aim 2. Evaluate changes in insulin, total cholesterol, high density lipoprotein cholesterol (HDL) low density lipoprotein cholesterol (LDL), triglycerides, LDL particle size, and high sensitivity C-reactive protein (hsCRP) in response to eating the PLM or LMP diets for eight weeks.

Hypothesis. Blood lipid, insulin, and hsCRP levels will improve, and the LDL particle size will increase compared to baseline in the PLM and LMP groups, but the two diets will not differ from each other.

RESEARCH DESIGN AND METHODS

The experimental plan is presented in Figure 1.

[figure not shown]

Figure 1. Study Schema

*Homeostatic model assessment of insulin resistance

Study Subjects

This study will enroll 36 overweight or obese male and female subjects. Subjects will be enrolled on the basis of the following eligibility criteria:

Inclusion Criteria

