We will attempt to retain program participants once randomized for study completion through the end of study visit. It is our desire to analyze results on all participants who were enrolled in the study. In accordance with the declaration of Helsinki/Tokyo/Venice/Hong Kong, participants have the right to withdraw from the program at any time for any reason. The investigator also has the right to withdraw participants from the program treatments in the event of inter-current illness, adverse experience, treatment failure, protocol violation, or other reasons. Should a participant decide to withdraw from treatment, all efforts will be made to complete and report follow-up observations as thoroughly as possible.

RISKS/BENEFITS

The study involves the following risks:

- **IV Procedures/Blood Draws:** There is the possibility of discomfort, pain, and bruising at the vein on the arm where the needle is inserted. There may also be a small risk of bleeding and a very small risk of infection at the site of the blood draw. Sterile technique and trained personnel minimize these risks.
- **Study Foods.** The meals provided during the study are foods that are ordinarily consumed by people and are cooked and stored using methods common in food preparation. The research dietitians and staff of the research kitchen are experienced in developing, preparing, storing, and dispensing study-specific food products developed to meet the needs of the study. Additionally, subjects will be asked to inform staff about any food allergies or intolerances. A dietary questionnaire is routinely administered at the screening visit when the study involves a meal service. Research dietitians are responsible for managing the dietary component of specific study protocols. A continuous quality assurance program is followed to check food item weights, recipe procedures, packaging of meals, and food temperatures. Documentation is maintained for each study. All Metabolic Kitchen staff members receive training in food sanitation and in research diet preparation. Therefore, there is no risk associated with the meals provided by the Pennington Metabolic kitchen.
- **Nutrition Counseling.** There is minimal risk associated with behavioral counseling. Sessions are confidential and the counselor is trained to minimize any discomfort that is associated with the discussions during the sessions.

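### Equivalence is the primary claim, but the plan defines no analysis set and makes no analytic use of its weekly compliance data

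*Combined protocol and SAP*

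**What the plan says.** Under Power and Sample Size the plan states: "Equivalence in blood glucose will be the primary outcome". Aim 1 words the same goal as non-inferiority, expecting improvement in "the PLM and LMP groups but the two diets will be non-inferior to each other". The sample size statement is: "This study has 80% power to show equivalence between the two groups with at least 15 subjects per group". The limit attached to it is 40 mmol × min/L, on the incremental glucose area under the curve (iAUC).

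The Statistical Analysis paragraph plans mixed models for change over the eight weeks. It names no intention-to-treat, per-protocol or adherent set, no equivalence test and no alpha. Its only sensitivity analysis concerns missing data.

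The one sentence on who is analysed is under Withdrawal of Subjects: "It is our desire to analyze results on all participants who were enrolled in the study". The same section lets the investigator withdraw participants for protocol violation, without saying whether their data remain in the analysis. Follow-up after withdrawal is mentioned only where the participant decides to leave treatment.

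On adherence, the Abstract says: "Compliance will be evaluated by the dietitian through monitoring of all foods and containers that subjects will be required to return". The Clinic Visits section repeats this at Visits 2 to 8, and Table 1 also marks compliance at Visit 9. In the statistical section, compliance monitoring appears only as support for the assumed standard deviation.

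**The concern.** In a superiority trial, subjects who do not follow their assigned regimen usually make the test conservative. In an equivalence or non-inferiority trial the effect is reversed: they pull the two groups together and make the hoped-for conclusion easier to reach. Subjects here eat at home for eight weeks, and the rationale section itself describes lack of compliance as common in lifestyle interventions.

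If equivalence is found and nobody has looked at adherent subjects, a reader cannot tell whether the diets act alike or whether they were not eaten as assigned. Nor is it fixed in advance which subjects count, because the fate of data from subjects withdrawn for protocol violation is open. Aim 2 also hypothesises no difference between diets, and its fasting outcomes (lipids, hsCRP) are exposed in the same way.

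**Working it through.** **Inputs from the documents.** Limit 40 mmol × min/L; 15 evaluable per group; 80% power; printed values 96 ± 12.5 (mixed meal) and 197 ± 28.2 (potato alone) from the cited 11-subject crossover study.

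**Assumptions, because the documents are silent.** Two one-sided tests (TOST) at one-sided 5%, so equivalence is declared when the 90% confidence interval lies within ±40. The SD range is 28.2 (the larger printed value, read as an SD) to 41.5 (12.5 read as a standard error: 12.5 × √11 = 41.5). A fraction f of each group contributes no diet contrast; no adherence rate is given.

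**The plan's own figure.** At a true difference of 0, TOST needs 10 per group at SD 28.2 (15 give 97% power) and 20 per group at SD 41.5 (15 give 65%). Exactly 80% at 15 per group needs an SD of about 36.5, which is not stated. So 15 is not reproduced from the printed inputs. That is a separate matter and this point does not depend on it, but it is why a range is shown.

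**Dilution.** Let the true difference in adherent subjects be 40, where TOST should declare equivalence 5% of the time. With all subjects analysed, the difference becomes θ = 40 × (1 − f). With SE = SD × √(2/15), 28 degrees of freedom and t = 1.701, equivalence is declared when the observed difference lies within ±L, where L = 40 − 1.701 × (estimated SE). The probability is Φ((L − θ)/SE) − Φ((−L − θ)/SE), averaged over the sampling distribution of the estimated variance.

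Rough check at f = 20% (θ = 32), treating the SE as known:
- SD 28.2: SE = 10.30, L = 40 − 17.52 = 22.48, Φ((22.48 − 32)/10.30) = Φ(−0.92) ≈ 0.18.
- SD 41.5: SE = 15.14, L = 40 − 25.75 = 14.25, Φ((14.25 − 32)/15.14) = Φ(−1.17) ≈ 0.12.

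Full calculation, probability of declaring equivalence:

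| f | SD 28.2 | SD 36.5 | SD 41.5 |
|---|---|---|---|
| 0 | 5% | 5% | 5% |
| 10% | 10% | 8.8% | 8% |
| 20% | 19% | 14.5% | 13% |
| 30% | 31% | 22% | 19% |

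At one-sided 2.5% and f = 20%, the rate rises from 2.5% to 7% (SD 41.5) to 11% (SD 28.2). Adding the extra variance from mixing adherent and non-adherent subjects changes the 5%-level result at f = 20% only to 13% to 18%. A smaller SD gives a larger inflation.

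**Allowing for the supervised meal.** If the comparison is the Visit 9 response and only half of the between-diet difference builds up over the eight weeks (an assumption), non-adherence erodes only that half: θ = 40 × (0.5 + 0.5 × 0.8) = 36. This equals the 10% row: about 8% (SD 41.5) to 10% (SD 28.2).

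**Cost of a smaller set.** With 12 per group and a true difference of 0, TOST power is about 48% (SD 41.5), 66% (SD 36.5) or 92% (SD 28.2).

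**The case against.** A reader might infer that the plan commits to claiming equivalence from an all-enrolled analysis alone. The documents do not support that. The sentence under Withdrawal of Subjects expresses a wish, in a paragraph about retention, and nowhere is it called the sole analysis. Because the investigator may withdraw subjects for protocol violation, some non-adherent subjects might leave the data altogether. What stands is that the analysed set is undefined.

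The best argument against the dilution mechanism is the test meal. Under Meal Tolerance Test, each subject receives the assigned meal in the clinic, at baseline and at Visit 9. The acute contrast between meals is therefore delivered whatever was eaten at home. This is correct and limits the point for a Visit 9 comparison. It does not remove it: the Statistical Analysis paragraph models change over eight weeks, and the part of the response that builds up over that time depends on adherence.

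A reader might also infer that the compliance data serve no purpose. They do operationally: all food is provided, returns are checked weekly and counselling targets barriers to adherence. This lowers the likely rate of non-adherence. The gap is confined to the analysis.

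Finally, a per-protocol set is selected after randomisation and is smaller. That is a good reason not to make it a second condition for success, but not a reason to omit it.

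**Conclusion.** The point holds as a gap in specification. The plan makes equivalence primary, defines no analysis set, leaves open what happens to data from subjects withdrawn for protocol violation, and gives the weekly compliance data no role in the analysis. For the modelled eight-week change, non-adherence favours the equivalence claim; for the acute response to the supervised meal it does so much less.

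At 20% non-contributing subjects, the illustration takes false equivalence from 5% to about 13% to 19%, or to about 8% to 10% if half of the effect is acute. These figures rest on an assumed test, alpha, SD and non-adherence rate, and on a true difference exactly at the limit. The direction does not depend on the SD or alpha chosen; the size does. The documents do not show that adherence will be poor or that a finding of equivalence would be false.

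**What to change.** In Statistical Analysis:

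- State that the primary analysis includes all randomised subjects, and that data from subjects withdrawn by the investigator, including for protocol violation, are kept and followed up where possible.
- Before group codes are opened, define a per-protocol set: both meal tolerance tests completed, and a pre-set share of the provided entrées eaten according to the returned-food record. The dietitian and kitchen staff know the allocation, so membership should follow from a fixed numerical rule and not from judgement.
- Run the same equivalence analysis in that set as a pre-specified supportive analysis. Report both confidence intervals against ±40 and qualify the equivalence conclusion if they disagree.

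The cost is SAP wording and one further run of the same model on data already collected. The drawbacks are the lower power shown above for 12 per group and the loss of protection by randomisation. For both reasons the per-protocol result should support the primary analysis and not act as a second hurdle.
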